3.2 Estimation of overall efficacy

Logistic regression will be used to assess the overall efficacy of the intervention, including data from all 142 facilities. We anticipate varying intervention effects per region and per facility level and depending on whether the facility was part of SBBC phase I or not, and possibly also varying intervention effects between combinations of these factors. Further, we anticipate time-varying intervention effects as well as clustering on two levels, birth (for multiples) and facility.

Thus, the full model will be a mixed-effects logistic regression model, incorporating the following:

Fixed effects:

- a) Time-varying intervention effects modelled using a continuous variable representing time since intervention start (set to zero for all baseline observations). To capture potential nonlinear effects, time will be modelled using splines. The spline-transformed time variable, f(t), will be interacted with an indicator for intervention status (intervention vs. baseline), i.e., I(intervention).
- b) Region-specific treatment effects, modeled through an interaction between region (five regions) and the intervention-by-time spline term, $I(\text{intervention}) \cdot f(t)$.
- c) Facility level-specific treatment effects, modeled through an interaction between facility level (three levels) and $I(\text{intervention}) \cdot f(t)$.
- d) Differing treatment effects between facilities that were part of SBBC phase I and those new in SBBC phase II, through interaction between SBBC-I (yes/no) and I(intervention) $\cdot f(t)$.
- e) All higher level interactions between region, facility level, SBBC-I, and $I(\text{intervention}) \cdot f(t)$.

Random effects:

f) Random effects (random intercepts and random intervention effects) for facilities and for births nested within facilities.

In Stata syntax, the full regression model looks like this:

```
i.region i.facility_level i.sbbc_phase1 i.intervention ///
i.intervention#c.s_time ///
i.region#i.intervention#c.s_time ///
i.facility_level#i.intervention#c.s_time ///
i.sbbc_phase1#i.intervention#c.s_time ///
i.region#i.facility_level#i.intervention#c.s_time ///
```

```
i.region#i.sbbc_phase1#i.intervention#c.s_time ///
i.facility_level#i.sbbc_phase1#i.intervention#c.s_time ///
i.region#i.facility_level#i.sbbc_phase1#i.intervention#c.s_time ///
|| facility_id: i.intervention i.intervention#c.s_time ///
|| birth_id: i.intervention i.intervention#c.s_time ///
, covariance(unstructured)
```

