In the (likely) case of convergence problems, the model will be reduced in the following order:

- 1. Reducing complexity in the random effects.
- 2. Reducing complexity in the fixed effects by removing higher order interactions.
- 3. Reducing complexity in the fixed effects by reducing the degrees of freedom for the splines of time, ultimately assuming linear effect of time.
- 4. After each reduction in fixed effects, try in the random effects again.

Regarding 1: Experience from SBBC phase I was that the clustering on birth level (for multiples) was difficult to account for without convergence issues. If the same problem is encountered here and not resolved by removing random intervention effects at two levels, we will resort to the same solution as used in phase I, i.e., including only one of the babies in births with multiples.

Once a model has been identified that converges successfully and shows no signs of numerical instability, we will proceed to reducing the fixed effects structure by optimizing Akaike's Information Criterion (AIC). Specifically, any parameter whose removal results in a reduction of the AIC by at least 2 will be excluded from the model. If possible, random effects will be reintroduced.

In SBBC-I, FHR at admission was by far the most important individual-level adjustment variable for perinatal deaths, and for maternal deaths, FHR at admission and ASB were most important. Referral-in (yes/no) was also of some importance. FHR at admission and referral-in are only available in the intervention period here and only on facility level (FHR also in a less informative variable than in SBBC-I), and this is also the case with preterm (yes/no). Thus, in addition to ASB (for maternal outcome), we will in the current analyses have to suffice with adjusting for birth weight (categorical including "missing" as a category), mother's age (non-linear effect), and multiples (yes/no), which all were found to have some adjustment effect in SBBC-I. Since we do not expect changes in the population during the study period, these adjustments will be mostly relevant for comparisons between regions, facility levels, and SBBC-I (yes/no), where changes in referral patterns among the participating facilities during the intervention may play a role.

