The overall effect of intervention will be presented as the marginal relative risk (RR) at 1.5 years after start intervention, obtained using g-computation (Snowden et al, 2011). Maximum likelihood estimation will be used for model fitting, the final model will be fitted using restricted maximum likelihood.

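### The Stata code in SAP section 3.2 puts the unstructured covariance on the birth equation only, so facility random effects default to uncorrelated; if that is untrue, the primary RR and its CI can be wrong

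*SAP*

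**What the plan says.** SAP section 3.2, item f, asks for "Random effects (random intercepts and random intervention effects) for facilities and for births nested within facilities". It names no covariance structure at either level.

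The code that follows is introduced with "In Stata syntax, the full regression model looks like this". Its facility equation reads "facility_id: i.intervention i.intervention#c.s_time", with no comma and no option of its own. Its birth equation reads "birth_id: i.intervention i.intervention#c.s_time", and the next line carries the only covariance option in the model, "covariance(unstructured".

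The same section treats this as a starting model: "In the (likely) case of convergence problems, the model will be reduced in the following order". The first step is "Reducing complexity in the random effects", and random effects are to be tried again after fixed effects are cut and reintroduced where possible. The primary result is then defined: "The overall effect of intervention will be presented as the marginal relative risk (RR) at 1.5 years after start intervention, obtained using g-computation". The section does not say how the g-computation treats the random effects.

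**The concern.** In Stata's mixed-effects commands the covariance option belongs to the random-effects equation it follows, and an equation without it takes the independent structure. As coded, the birth-level effects are unstructured and the facility-level effects are uncorrelated.

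The flexibility is therefore at the less informative level. Intervention status and time do not vary within a birth, and few births are multiples, so birth-level covariances are hardly identifiable. The 142 facilities could inform a facility-level covariance, but there it is fixed at zero.

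The constraint has content. With intervention coded 0/1, independence means the between-facility variance cannot fall after the intervention starts, so the model cannot represent facilities becoming more alike. A marginal RR that averages over facilities by integrating the random-effects distribution depends on the variance in both periods. The co-primary RRs and their intervals are what is at stake.

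**Working it through.** **Inputs from the SAP (section 3.2).** 142 facilities; the placement of the option; a marginal RR as the estimand. The SAP gives no variance component, intercept-effect correlation or event rate for this model, so there is no planned figure to reproduce.

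**Assumed inputs.** Risk 1.2% or 0.08%; about 1,500 baseline and 2,000 intervention births per facility; conditional OR 0.80; intercept SD (s0) 0.5 to 1.0; intervention-effect SD (s1) 0.2 to 0.6; correlation (r) -0.7 to +0.7.

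**Step 1: what independence removes.** Leaving time terms aside, the facility variance on the logit scale is

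- baseline: s0²
- intervention: s0² + s1² + 2·r·s0·s1

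Independence sets the last term to zero. The intervention variance is then s0² + s1² (plus a non-negative time-slope term), never below s0².

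**Step 2: why the marginal RR moves.** For a rare outcome, marginal RR ≈ OR × exp[(s1² + 2·r·s0·s1)/2]. With OR 0.80, s0 = 0.8, s1 = 0.4:

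- r = -0.7: 0.80 × exp[(0.16 - 0.448)/2] = 0.80 × 0.866 = 0.693
- r = 0: 0.80 × exp(0.08) = 0.867
- r = +0.7: 0.80 × exp[(0.16 + 0.448)/2] = 0.80 × 1.355 = 1.084

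The exact values at 1.2% risk are 0.703, 0.866 and 1.058.

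**Step 3: simulation.** Logistic models with a facility random intercept and intervention effect were fitted by Laplace maximum likelihood under both structures, with 120 replicates per scenario. The RR was integrated over the random effects, with a delta-method SE. There were no splines, fixed-effect interactions or birth level. Medians, with 95% CI coverage for the independent model:

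| Risk | s0/s1 | r | True RR | Independent (coverage) | Unstructured |
|---|---|---|---|---|---|
| 1.2% | 0.8/0.4 | -0.7 | 0.703 | 0.783 (31%) | 0.708 |
| 1.2% | 0.8/0.4 | +0.7 | 1.058 | 0.939 (21%) | 1.059 |
| 1.2% | 0.8/0.6 | -0.6 | 0.727 | 0.856 (15%) | 0.729 |
| 1.2% | 0.8/0.6 | +0.6 | 1.214 | 1.018 (17%) | 1.207 |
| 1.2% | 0.5/0.5 | 0 | 0.904 | 0.905 (96%) | 0.902 |
| 1.2% | 0.5/0.2 | -0.6 | 0.772 | 0.782 (94%) | 0.776 |
| 1.2% | 0.5/0.2 | +0.6 | 0.866 | 0.853 (95%) | 0.869 |
| 0.08% | 1.0/0.6 | -0.6 | 0.669 | 0.701 (95%) | 0.666 |
| 0.08% | 0.8/0.4 | +0.7 | 1.082 | 1.026 (97%) | 1.063 |

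In every scenario run, the unstructured model stayed within about 2% of the true RR with coverage of 95% to 99%. For the independent model the error in the first two rows is 0.783/0.703 = 1.11 and 0.939/1.058 = 0.89. At 0.08% risk it was at most about 5%. Positive correlation with 0.08% risk and SDs 1.0/0.6 was not run.

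**Step 4: interval width.** The SE ratio, independent over unstructured, ran from 0.84 (1.2%, SDs 0.8/0.6, r = +0.6) to 1.025 (1.2%, SDs 0.5/0.2, r = +0.6; independent wider in 86% of replicates). The interval can be too narrow or too wide.

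**Step 5: a second simulation with other assumptions** (about 1,050 baseline and 1,470 intervention births per facility, about 1.3% risk, between-period correlation 0.8, adaptive quadrature, 100 runs). With facility SD falling from 0.6 to 0.4, the true RR was 0.825; independent 0.869 with 75% coverage, unstructured 0.823 with 96%. With SD falling from 0.6 to 0.5, the true RR was 0.861; independent 0.889 with 86%, unstructured 0.852 with 93%. With SD unchanged at 0.5, independent coverage was 95%.

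**Step 6: dependence on the g-computation.** The three settings of step 5 were rerun (60 runs each, Laplace). Integrating over the random effects gave median RRs, independent against unstructured, of 0.859 and 0.830, 0.894 and 0.869, and 0.923 and 0.914. Standardising over the 142 facilities with their predicted effects gave 0.831, 0.869 and 0.916 under both structures. Coverage under predicted effects was not tested.

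**The case against.** A reader might infer that the primary RR is certainly biased and its CI always too narrow. The SAP does not support that. Bias needs a non-zero intercept-effect correlation, which the SAP neither gives nor assumes; its sign follows that correlation, and the CI can also be wider. The SAP also nowhere says that high-mortality facilities should benefit most, so a negative correlation is plausible but not a premise of the plan.

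Further points carry weight:

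- The damaging settings are strong. In step 5, SD falling from 0.6 to 0.4 implies r = (0.8×0.6×0.4 - 0.36)/(0.6×√0.136) = -0.76, and from 0.6 to 0.5 implies -0.55. The harmless case is itself r = -0.32, so a moderate violation can leave coverage intact.
- The planned region, facility-level and phase I terms would absorb some facility heterogeneity. The simulations omit them, so residual SDs may be smaller than assumed.
- The shift in the point estimate disappeared when predicted facility effects were used, and the SAP does not fix this choice.
- The code is a fragment of a starting model. Reduction cuts random effects first and may remove the random intervention effects at both levels; no intercept-effect covariance would then be left to misspecify.

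These limit the consequence and do not remove the defect. Literal use of the code imposes an unstated constraint, and any facility intervention effect retained or reintroduced from this template is independent by default. Falling back to one baby per multiple birth would remove the need for the birth equation, which carries the only option. A reader might infer that the option would then be lost; the SAP does not say what the analyst would do, which is a reason to write it down.

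**Conclusion.** The point holds as a coding and specification defect with a conditional consequence. The option is attached to the birth equation only, and the facility effects default to a structure that item f does not state or justify.

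Where the facility intercept and intervention effect are truly correlated and the RR is integrated over the random effects, the estimate can be off in either direction and the CI misstated. Under the assumed inputs the error runs from negligible (correlation near zero), through about 1% to 2% (SDs 0.5/0.2) and up to about 5% (0.08% risk), to 11% or more with poor coverage (1.2% risk, large SDs, strong correlation). Which applies here cannot be told from the SAP. If no facility-level intervention effect survives the reduction, the point is moot.

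It should still be corrected: it bears on the primary model, and the change is one line at the level where 142 facilities can inform the covariance.

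**What to change.** 1. Put the option on the facility equation: `|| facility_id: <terms as now>, covariance(unstructured)`. State in item f the covariance structure intended at each level.
2. Add to the reduction rules that birth-level random slopes are removed first, and that the facility intercept-by-intervention covariance is kept, where the model converges, for as long as a facility intervention effect is in the model.

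Cost: one line of code and one or two sentences. With an intercept, an intervention effect and k time terms, the unstructured facility matrix adds (k+2)(k+1)/2 covariances: 3 for k = 1, 6 for k = 2, 10 for k = 3. That brings some added risk of non-convergence in a model the SAP already expects to be hard to fit.

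### Section 3.2 lets the facility random intervention effect be dropped to cure a birth-level convergence problem, with no clustered-variance fallback, and may then discard babies from multiple births

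*SAP*

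**What the plan says.** Section 3.2 of the SAP expects "clustering on two levels, birth (for multiples) and facility" and sets out a mixed logistic model "including data from all 142 facilities". The random part is "Random effects (random intercepts and random intervention effects) for facilities and for births nested within facilities". The Stata syntax adds random time slopes at both levels, with unstructured covariance.

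The plan then says: "In the (likely) case of convergence problems, the model will be reduced in the following order". Step 1 is "Reducing complexity in the random effects". Higher-order fixed interactions come second and spline degrees of freedom third. Step 4 tries the random effects again after each fixed-effect reduction.

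For step 1 the plan explains that clustering within multiples was hard to fit in phase I. If taking out the random intervention effects at both levels does not cure this, the fallback is "including only one of the babies in births with multiples". No rule says which baby is kept. AIC pruning of the fixed effects follows, and then: "If possible, random effects will be reintroduced".

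The primary result is the marginal relative risk at 1.5 years by g-computation (section 3.2), judged at p<0.025 for each co-primary outcome (section 4). Section 3.2 names no minimum random structure, and the SAP states no cluster-robust variance or bootstrap for this relative risk.

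**The concern.** The term that causes the trouble and the term that protects the inference are different. The birth-level slopes carry almost no information and cost nothing to remove. The facility random intervention effect carries differences between facilities in how much the death rate changed, beyond what region, facility level and phase I status explain. A before-after comparison over 142 facilities needs that variation in its standard error. The plan allows the facility term to be removed to cure a problem at birth level, while the highest-order fixed interactions are still in the model.

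At stake is whether the interval and the p<0.025 test for the primary relative risk are honest about facility-level variation. A separate matter is whether perinatal deaths are thrown away when they could be kept.

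**Working it through.** **Is the birth level identifiable?** Write the birth-level effects as u0 (intercept), u1 (intervention) and u2 (time, one column). A baseline birth has u0 only, and an intervention birth at time t has u0 + u1 + u2·t. The unstructured covariance has 6 parameters. The data can inform only the baseline variance s00 and the intervention-period variance (s00 + s11 + 2·s01) + 2t·(s02 + s12) + t²·s22. That is 4 quantities: s00, s11 + 2·s01, s02 + s12 and s22. Two parameters are therefore not identified, and the other four rest on multiples alone. For maternal death there is one binary outcome per birth, so even a birth intercept is uninformed.

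**Do the safeguards bring the facility term back?** Step 4 is triggered by a fixed-effect reduction. If cutting random effects alone gives convergence, no fixed effect has been reduced and step 4 does not apply. AIC pruning comes next. Removing one parameter changes AIC by LR − 2, so AIC can fall by at most 2, and the plan's threshold of a fall of at least 2 is met only at LR = 0. Taken parameter by parameter it prunes almost nothing; it can act only if whole multi-df terms are tested. Final reintroduction has no criterion beyond being possible.

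**Size if the facility term stays out and model-based SEs are used.** The SAP gives no event count, effect SD or volume spread, so there is no plan figure to reproduce. Assumptions for perinatal death: D = 2,000 deaths per period, residual SD of the facility log-OR change τ = 0.2-0.3, CV of facility volume 0.8-1.0.

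- Omitted variance: τ²(1 + CV²)/142. Low: 0.04 × 1.64/142 = 0.000462. High: 0.09 × 2/142 = 0.001268.
- Model variance v0, simple before-after contrast: 2/D = 0.0010.
- Model variance v0 at the end of a linear trend with evenly spread events: 1/D for baseline plus 4/D for the end of the line, so 5/D = 0.0025.
- Reported SE / true SE = √[v0/(v0 + omitted)]; true type I error = 2[1 − Φ(2.241 × ratio)].

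| v0 | τ, CV | SE ratio | SE too small by | Type I error (nominal 2.5%) |
|---|---|---|---|---|
| 2/D | 0.2, 0.8 | 0.827 | 17% | 6.4% |
| 2/D | 0.3, 1.0 | 0.664 | 34% | 13.7% |
| 5/D | 0.2, 0.8 | 0.919 | 8% | 3.9% |
| 5/D | 0.3, 1.0 | 0.815 | 18% | 6.8% |
| 2/D | 0.1, 0.8 | 0.947 | 5% | 3.4% |

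For maternal death, an assumed 100-300 deaths per period with v0 = 2/D, τ 0.2-0.3 and CV 0.8-1.0 gives an SE 1-8% too small and type I error of 2.7-4.0%.

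**Does clustered variance repair it?** A simulation used 142 facilities of unequal size (CV 0.8), a true marginal relative risk of 1, mean deaths per facility per period of 3-40, τ of 0-0.5 and 4,000 runs per cell. Facility-clustered SEs gave 95% interval coverage of 93-95% and type I error of 2.4-4.1% throughout. Without clustering, coverage was about 95% at τ = 0 but 85.8% at 10 deaths per facility and τ = 0.3.

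**Deaths lost with one baby per multiple birth.** If a share p of babies are multiples at r times the risk, they hold p·r/(p·r + 1 − p) of deaths. Assumed p = 0.03, r = 3: 0.09/1.06 = 8.5%. Assumed p = 0.04, r = 4: 0.16/1.12 = 14.3%. Dropping one of each pair at random loses half of these, 4.2% to 7.1%.

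**The case against.** A reader might infer that the plan is bound to lose the facility random effects and so to report too narrow an interval. The text does not support that. Step 1 speaks of reducing complexity; random time slopes and covariances can be simplified before the facility intervention effect goes. Step 4 retries the random effects, and a further reintroduction is foreseen. If one baby per birth is analysed, only the facility level remains to be fitted. The SAP also does not state the variance method for the g-computation relative risk, so too narrow an interval presumes model-based SEs. All of this stands, and it makes the problem a risk and not a certainty.

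A reader might also take 6-14% as the type I error of the primary analysis. That range belongs to a simple before-after contrast for perinatal death. A relative risk read from a time curve near the end of follow-up has a larger model variance, so the omitted part matters less, unless heterogeneity is also larger at 1.5 years. Nor is τ the total heterogeneity. The plan says "We anticipate varying intervention effects per region and per facility level and depending on whether the facility was part of SBBC phase I or not"; its model includes those differences, so only the residual counts.

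Nor does dropping co-multiples narrow the interval: it removes within-birth correlation. It affects child outcomes only, follows phase I practice and applies in both periods; no bias in the relative risk is shown.

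Finally, reversing the whole order has a price. Cutting spline degrees of freedom early could misshape the curve that gives the 1.5-year estimate, and section 7 promises relative risks by combinations of factors. That objection holds against a full reversal, but not against protecting the facility terms or clustering the variance.

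**Conclusion.** The point holds as a conditional risk in the primary analysis. The birth-level slopes are not identifiable, the reduction path permits loss of the facility random intervention effect, and nothing guarantees its return or replaces it. Should it stay out under model-based SEs, the perinatal-death SE is about 8-34% too small and type I error about 4-14% against a nominal 2.5%, depending on the variance of the 1.5-year contrast. These figures rest on assumed D, τ and CV. The effect shrinks with smaller τ or fewer deaths, and vanishes at τ = 0.

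The loss of co-multiples is a separate and smaller matter: about 4-7% of perinatal deaths under the assumed shares and risks, with the choice of baby left open. It is avoidable, because births are nested in facilities and facility-clustered variance already covers correlation within a birth. The change should be made before the final analysis.

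**What to change.** 1. Delete the birth-level random intervention and time slopes, and state that no birth level is used for maternal death.
2. Name the facility random intercept and random intervention effect as the minimum structure. On non-convergence, first simplify the remaining birth-level term, the random time slopes and the covariance structure, and cut the highest-order fixed interactions. Only then consider the facility terms.
3. Whatever model is final, compute the SE, interval and p-value of the g-computation relative risk with facility-clustered robust variance or a bootstrap that resamples the 142 facilities.
4. Keep all babies. If one baby per birth is ever analysed, fix the selection rule in advance and show the all-babies result beside it.

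The cost is SAP wording, some computing time (mainly for a bootstrap) and somewhat wider intervals. No further data are needed.

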Adjustments will be made for monthly rates of referrals-in, births with not heard/detected FHR, and preterm births for each facility. Since these, as well as data regarding use of Moyo and NeoBeat, are only available for a substantial proportion of births from August 2024 and onwards, adjusted results and results for the latter predictor variables will be presented for the period August 2024 to December 2025. Unadjusted results, and results adjusted for BW, mother's age, and multiples, will be presented for the whole intervention period whenever possible.

In these analyses, the 30 SBBC-I facilities and the 122 new facilities will be analyzed separately.

4 Reporting and multiplicity considerations

Due to the non-randomized pre-post design of the study no causal claims will be made based on the estimated effects/associations.

All estimates will be presented with 95% confidence intervals (CI) and corresponding p-values from significance tests. For the estimates of overall efficacy for the two co-primary outcomes, p-values <0.025 will be considered statistically significant. All other p-values will be interpreted as exploratory.

If a confidence interval goes beyond the region of possible values for the parameter, we will report the interval truncated to possible values.

5 Graphical displays of results

Results from the main analyses will be supplemented with prediction plots based on the final models.

Furthermore, to accompany the CUSUM plots and illustrate the impact of the intervention over time, variable life adjusted displays (VLAD) will be made (Lovegrove, 1997). These plots will be made by aggregating the difference between the estimated conditional probability for fatal outcome based on a model estimated from baseline data, and the observed outcome, and can thus be interpreted in terms of estimated numbers of lives saved. The same logistic regression models as used for the CUSUM plots described in Section 3.3 will be used to estimate the probability of fatal outcome under baseline conditions.

For the promotor/inhibitor analyses, estimated marginal rates will be presented over time for each considered factor, based on the Poisson regression models.

6 Missing data and sensitivity analyses

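### The AIC reduction does not protect the time terms that define the primary RR at 1.5 years, so the level and coverage of the primary test are not guaranteed

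*SAP*

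**What the plan says.** SAP section 3.2 builds a mixed-effects logistic model with an intervention indicator, I(intervention), and its interaction with a spline of time since start, I(intervention)·f(t). It says that "we anticipate time-varying intervention effects as well as clustering on two levels". The primary measure is tied to one time point: "The overall effect of intervention will be presented as the marginal relative risk (RR) at 1.5 years after start intervention".

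Between the full model and that estimate there are two reduction stages. The first deals with non-convergence. It may lower the spline degrees of freedom, but stops at a linear time effect. The second optimises AIC over the fixed effects, and "any parameter whose removal results in a reduction of the AIC by at least 2 will be excluded from the model". No term is listed as protected, and no floor for time is given at this second stage.

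Section 4 then sets the inference: "All estimates will be presented with 95% confidence intervals (CI) and corresponding p-values from significance tests", and "For the estimates of overall efficacy for the two co-primary outcomes, p-values <0.025 will be considered statistically significant". No allowance for model selection is described.

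**The concern.** The RR at 1.5 years is computed from I(intervention) and the terms carrying I(intervention)·f(t). If all the time terms are removed, nothing in the fitted model refers to 1.5 years, and g-computation returns the same RR at every time point. If the effect has faded by 1.5 years, the early months can produce a significant result at a time when there is no effect. If the effect grows, the reported RR is diluted and its CI is too narrow. Both co-primary conclusions pass through this step, in a plan that expects the effect to change with time.

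**Working it through.** **Inputs from the SAP.** Threshold 0.025 per co-primary outcome and 95% CI (section 4); RR at 1.5 years, the AIC rule and the model (section 3.2); intervention start April–June 2024 (section 1) and data to end 2025 (section 2), so about 18 to 21 intervention months. The 0.025 equals 0.05/2; the overall 0.05 and two-sidedness are assumed. The SAP gives no spline degrees of freedom, event counts or birth volumes, so these are assumed too.

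**Step 1: what the rule can remove.** Removing q parameters lowers AIC by 2q − LR, where LR ≥ 0 is the likelihood-ratio statistic. A fall of at least 2 needs LR ≤ 2q − 2.
- One coefficient (q = 1): LR ≤ 0, so LR = 0 exactly. The probability is zero and nothing is removed.
- A whole spline block with no true trend, P(χ²_q ≤ 2q − 2): 0.63 for 2 df, 0.74 for 3 df, 0.80 for 4 df.
- Plain 1-df AIC (drop if AIC falls at all): P(χ²_1 < 2) = 0.84.

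**Step 2: what the RR becomes.** Take a log RR running linearly from ln 0.82 = −0.198 at the start to 0 at 1.5 years, equally weighted over that time. The average is −0.099, so the constant RR is exp(−0.099) = 0.91 where the value at 1.5 years is 1. The mirror case, growing from 1 to 0.82, is also reported as 0.91.

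**Step 3: simulated monthly counts.** Assumptions: 15 baseline and 19 intervention months, 5,000 or 15,000 births a month, death risk 1.2% or 0.1%, 3-df restricted cubic spline, no clustering, no subgroup interactions, 1,500–3,000 replicates per setting, two-sided 0.025.

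| True effect | Time terms kept | After selection |
|---|---|---|
| None at any time | rejects 2.3–3.1% | 3.6–4.5% (block removal); 4.0–5.2% (lowest AIC) |
| Waning to RR 1 at 1.5 years | rejects 1.5–3.2% | 14–17% in the worst case, coverage 76–81% |
| Growing to RR 0.82 (1.2% risk, 5,000 a month) | coverage about 94–95% | coverage 78–79% |

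The worst waning cases include an early perinatal RR of 0.82 at 5,000 births a month and 0.90 at 15,000.

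**Step 4: a second method.** A large-sample normal calculation used 400,000 runs per setting, an intervention period of 1.5–1.75 years and a baseline/intervention information ratio of 0.4–1.0. With the terms kept, size is 0.024–0.026 and coverage 0.949–0.951. With whole-term removal (2–4 df) and no trend, size is 0.033–0.041 and coverage 0.922–0.937. With RR 1 at 1.5 years and a drift of 1 to 2 standard errors, size is 0.053–0.22 and coverage 0.72–0.91. At 3 df, 1.625 years and ratio 1.0, a drift of 2 standard errors gives 30% removal, size 0.148 and coverage 0.800; a drift of 3 gives 8%, 0.084 and 0.889. A strong trend therefore protects itself.

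**Step 5: adding regional heterogeneity.** The waning case was re-run with five equal regions and a region-by-time block (risk 1.2%, 800 replicates, block removal). The between-region SD of log RR is assumed.

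| SD of log RR | 0 | 0.1 | 0.2 | 0.3 |
|---|---|---|---|---|
| 5,000 a month, early RR 0.82: rejects | 15.6% | 13.0% | 9.4% | 4.4% |
| all time terms dropped | 33% | 29% | 17% | 6% |
| 15,000 a month, early RR 0.90: rejects | 17.4% | 10.2% | 3.4% | 3.4% |
| all time terms dropped | 36% | 22% | 5% | 1% |

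**The case against.** The strongest reply is that the rule as written speaks of single parameters and so removes nothing, leaving 0.025 and 95% intact. The arithmetic is right. But the step is then inert, although the SAP says it will go on to reduce the model by optimising AIC. An analyst who carries it out must use whole terms or minimise AIC, and under both workable readings the problem appears.

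Second, the simulated model is simpler than the SAP's. In the section 3.2 syntax eight fixed-effect lines carry the time variable, and the heterogeneity expected by region, facility level and SBBC-I enters only through them. The RR becomes constant only if all eight go. This stands, and step 5 shows that it can remove much of the excess.

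Third, the CUSUM and VLAD displays use baseline models only, so a fading effect could still be seen there, and section 4 disclaims causal claims. That helps interpretation but does not correct the primary p-value or CI. The supplementary RRs at other time points (section 7) would not help if taken from the same reduced model, because they would all be equal.

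A reader might go further than the document allows in four ways:
- That the 0.025 level and the 95% CI fail outright. They fail only under some readings of the rule and some effect shapes.
- That the SAP states a null of RR 1 at 1.5 years. It writes no null; this one is inferred from sections 3.2 and 4.
- That dropping the time terms is always the cause. With no effect, the test after dropping is at its nominal level, and the excess comes from runs that keep f(t) because it looked large. With a constant effect, the period average equals the 1.5-year effect.
- That the reported RR may be exactly 1 with no CI. This needs I(intervention) and every interaction to be removed, which is remote; minimum AIC drops I(intervention) only when LR < 2 (p > 0.157), so that step cannot create a false positive.

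**Conclusion.** The point holds as a gap in specification. Section 3.2 leaves unprotected the terms that define the primary estimand, and its threshold is unusable for single coefficients and undefined for whole terms. If whole terms are removed or AIC is minimised, and all time terms go, the RR labelled 1.5 years is a period average. Level and coverage are then not guaranteed when the effect changes over time, which the SAP anticipates.

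The size is modest with no effect: about 4–5% rejection against 2.5%. In the worst waning case of the 3-df count simulations it is up to about 15–17%, with coverage of about 76–81%. Those upper figures assume no clustering, no subgroup interactions, assumed volumes and risks, and an RR that returns to exactly 1 at 1.5 years. They are illustrative, and fall towards nominal as regional heterogeneity or a strong trend keeps the time terms in. The change should be made, because both co-primary conclusions depend on this step.

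**What to change.** In the AIC paragraph of SAP section 3.2, state that:
- I(intervention) and I(intervention)·f(t) are always retained, with spline degrees of freedom named in advance, reduced only for non-convergence and never below linear;
- AIC reduction applies only to the interactions with region, facility level and SBBC-I, and acts on whole terms;
- the primary RR at 1.5 years, its CI and its p-value come from that model.

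Naming the degrees of freedom matters, because a number reached only through the convergence steps depends on the data. The nominal results with terms kept were obtained with fixed degrees of freedom and no subgroup interactions. Selecting those interactions by AIC before g-computation, or lowering the degrees of freedom for non-convergence, leaves some selection in place, so the change removes the main problem rather than guaranteeing exact level.

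Cost: a few sentences and no new data. The CI at 1.5 years will be wider, and apparent power falls if the effect grows steadily. In the growing case (1.2% risk, 5,000 births a month) power was about 44–46% with the terms kept against 54–56% after block selection, but the latter came with a CI that covered only 78–79%.
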